Spirometry equipment will be provided to each study site to perform all spirometry assessments for CVT-301-naïve patients and [CVT-301-009](#) patients at SV1, SV2 (if necessary) and TV1 (all patients). All other spirometry assessments will be collected during the DLco and spirometry visits that take place at the pulmonary function lab. Spirometry data collected at pulmonary function labs will be reviewed immediately by a pulmonologist on site for safety signals and then sent to and reviewed by a central Pulmonary Function Testing reviewer (TechEd Consultants).

11.1.7. Carbon Monoxide Diffusing Capacity (diffusing capacity of the lungs for carbon monoxide-DLco)

Patients will undergo DLco assessments, which will be acquired in accordance with ATS criteria ([Miller et al., 2005](#)), at a dedicated pulmonary function facility after SV2 (and prior to TV1; 301-naïve patients and [CVT-301-009](#) patients), within 2 weeks prior to TV3, TV4, TV5, and TV6, and at 4 to 5 weeks after TV6, as described in the [Appendix 3](#) through [Appendix 10](#). These assessments should be performed while the patient is in the ON state (as reported by the patient to the pulmonary technician). Pulmonary function facility technicians will perform a slow vital capacity maneuver, followed by DLco, and then spirometry. The pulmonary facilities will use

their own equipment to perform all necessary pulmonary function testing relevant to DLco acquisition.

DLco and slow vital capacity maneuvers will be assessed and processed in accordance with ATS/ERS standards. Spirometry procedures will be conducted at the same visits in the same manner as those conducted at clinical sites in accordance with ATS criteria (see [Section 11.1.6](#)).

All DLco data collected at pulmonary function labs will be sent to and reviewed by a central Pulmonary Function Testing reviewer (TechEd Consultants).

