PDQ-39 (in ON state)	X									
PHQ-9 (in ON state)	X									
AWQ and DDS-PC (in ON state)	X									
Physical examination (brief)	X									
UPDRS Parts 1 and 2 (preferably in ON state)	X									
S&E ADL (preferably in ON state)	X									
UPDRS Part 4 (Questions 32-35 and 36-39) (preferably in ON state)	X									
Electrocardiogram		X ³								
Standard and orthostatic BP and HR		X ³				X		X		
Respiratory rate		X ³		X		X	X	X		
Spirometry	X ⁴	X			X		X	X		

Procedures	Arrival	Pre-dose	Time 0 (Dosing) ¹	10 min Post-dose	15 min Post-dose	20 min Post-dose	30 min Post-dose	60 min Post-dose	End of TV1	Post-TV1 Telephone Contacts
Clinical laboratory tests (including serum pregnancy test, if applicable)	X ^{3,5}									
C-SSRS	X ^{3,4}									
Epworth Sleepiness Scale	X ^{3,4}									
QUIP	X ^{3,4}									
Impact of Parkinson's OFF Episodes Patient Survey	X ^{3,4}									
Review inhaler training	X									
Distribute PD Diary and Inhaled Dosing Log and review instructions for completion ⁶	X									
Distribute study drug kits	X									
Self-administration of study drug (in OFF state)			X ¹							
Monitor for AEs	X									
Schedule next visit									X	
Post-TV1 telephone contact: call patient 1-3 days after TV1										X
Post-TV1 telephone contact: call patient 1 week before TV2										X

¹First dose of study medication preferably occurs between 2 and 5 hours after patient has taken normal morning dose of PD medication and after all pre-dose assessments are complete.

²DLco is to be performed in a dedicated pulmonary facility and includes slow vital capacity maneuver, DLco, and spirometry.

³Procedures can be done at any point after arrival and before dosing.

⁴Preferably in the ON state.

⁵Document whether patient is fasting (≥4 hours after last snack or meal).

⁶The PD Diary is to be completed for the 3 consecutive days prior to TV2; the Inhaled Dosing Log is to be completed daily through TV6.

Appendix 6: Time and Events Table-Treatment Visit 2 (TV2) for all Patients (1 Month [4 Weeks ±5 days] after TV1)

Procedures	Arrival	Pre-dose	Time 0 (Dosing)¹	10 min Post-dose	20 min Post-dose	30 min Post-dose	60 min Post-dose	End of TV2	Post-TV2 Telephone Contact
Collect, review, sign, and date PD Diary and Inhaled Dosing Log	X								
Collect empty capsules, inhalers, and unused supplies	X								
Record any changes in usual PD medication dose/regimen	X								
Record time of patient's prior usual PD medication dose	X								

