## Statistical Analysis Plan

### 8. EFFICACY

The efficacy evaluation defined below includes data from the patients who were previously enrolled in the CVT-301-004 study and for the CVT 301 naïve patients (including patients from CVT-301-005 observational arm). The data from patients who were enrolled to study CVT-301-003 or CVT-301-009 will not be included in the efficacy summaries and will be listed only.

In general, for the purpose of the efficacy analyses, the visits will be pooled as follows:

Treatment/study group	Study CVT-301-004				Study CVT-301-004E			
	Baseline visit	Week 4 visit	Week 8 visit	Week 12 visit	Baseline visit	Month 1 visit	Month 3-9 visits	Month 12 visit
CVT-301-004, CVT-301 group	Baseline	Month 1	not used	Month 3	not used	not used	Months 6-12	not used
CVT-301-004, placebo group	not used	not used	not used	not used	Baseline	Month 1	Months 3-9	Month 12
CVT-301 naïve patients	NA	NA	NA	NA	Baseline	Month 1	Months 3-9	Month 12
CVT-301-005, Observational, Arm	NA	NA	NA	NA	Baseline	Month 1	Months 3-9	Month 12

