## Statistical Analysis Plan

### 9. SAFETY

The population used for safety analyses will be the Safety Population. The analyses are outlined below. The safety evaluation defined below includes data from all patients included in the Safety population.

For the statistical analysis of the spirometry data, the visits will be pooled as described in [Section 8](#). Otherwise, all safety data will be presented in the summaries,

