#### 9.1. SPIROMETRY

For CVT-301-naïve patients and [CVT-301-009](#) patients, spirometry will be assessed at the neurology sites for screening and TV1 and the pulmonary sites will be exclusively responsible for the conduct of spirometry after TV1 (within 2 weeks prior to the 3-, 6-, 9-, and 12-month visits, and 4 to 5 weeks following completion of Treatment Visit 6 [TV6]). For patients from [CVT-301-004](#), spirometry will be assessed at the neurology sites at TV1, and the pulmonary sites will be exclusively responsible for the conduct of spirometry after TV1 as described for the CVT-301-naïve patients. Spirometry data obtained in the study site will reviewed by a central spirometry laboratory (Biomedical Systems, Inc.) which will provide a quality over read of all evaluations based on acceptability and repeatability metrics in accordance with ATS criteria. FEV1, FVC and FEV1/FVC ratio will be recorded from the single “best test” (based on effort with highest summed FEV1 and FVC). Variables will include the absolute FEV1, FVC, and FEV1/FVC ratio and FEV1 and FVC expressed as % of predicted value.

The variables from pulmonary laboratory will include the FEV1, FVC, FEV1/FVC ratio, DLCO, IVC, SVC and VA. FEV1 and FVC expressed as % of predicted value, predicted DLCO, hemoglobin (Hb) adjusted predicted DLCO, and DLCO expressed as % of these predicted values will be calculated per the method in [section 6.2](#). The following analysis will be performed:

All the parameters collected at the pulmonary laboratory as well as the % of predicted DLCO and % of Hb adjusted predicted DLCO will be summarized descriptively by treatment group and overall. In addition, the data will be summarized by treatment/study group.

- Change from baseline to other visits for each parameter.
- Number and percentage of patients with FEV1/FVC < 60% and <70% by visit
- DLCO data will also be provided to indicate whether specific determinations met American Thoracic Society (ATS) quality criteria. The proportion of DLCO/spirometry data measurements meeting or not meeting ATS quality criteria will be summarized by treatment group and overall.

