## Statistical Analysis Plan

- Categories of changes (<-50%, -50% -<-40%, -40% -<-30%, , -30% -<-20%, , -20% -<-10%, -10% -<-10%, 10% -<20% , 20% -<30% , 30% -<40% , 40% -<50%, >=50%) from baseline for FEV1, FEV, FEV1/FVC ratio and DLCO by visit. The summary for FEV1 will also be provided by smoker status.

The descriptive summaries will be repeated for the subset of assessments meeting the ATS quality criteria.

Another subset analysis will be performed by excluding the DLCO data from patients with a very high intra-individual variability. For the purpose of this analysis, all patients who have a co-efficient of variation (CV) value >7.5% for FEV1 will be excluded. The CV will be calculated for each patient as standard deviation divided by the mean.

In addition to the descriptive statistics, the changes in the FEV1, FEV1/FVC ratio, and DLCO values within each treatment group and differences between the treatment groups will be estimated with MMRM. The model will include the treatment group (CVT-301 DL1 or CVT-301 DL2), treatment/study group (patients who received inhaled CVT-301 in CVT-301-004 study, patients who received placebo in CVT-301-004 study and CVT 301 naïve patients), visit (visits at 1, 3, 6, 9, and 12 months), the stratification variables (Hoehn and Yahr stage and screening FEV1 and/or FEV1/FVC) and the interaction between the treatment group and visit as fixed factors. The baseline spirometry value will be included as a covariate. An unstructured covariance structure will be applied for MMRM. In case the model will not converge with the unstructured covariance structure, the heterogeneous compound symmetry (CSH) or the heterogeneous Toeplitz structure (TOEPH) will be used instead. If the unstructured covariance structure will be used, the denominator degrees of freedom will be computed using the Kenward-Roger method. In case of other covariance structures, the BETWITHIN option will be used for the denominator degrees of freedom. The least square (LS) mean, standard error, and LS mean difference for the changes from baseline within each treatment group and overall, and between the treatment group at each visit; along with the 95% confidence interval (CI) will be provided in a table. Treatment group difference will be assessed with a 2-sided alpha level of 0.05, unless specified otherwise.

The SAS code planned for the analysis is outlined below.

```
proc mixed data=&data;
class pdsevl fevlbl trta stdygrp avisit usubjid;

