## Statistical Analysis Plan

The safety population will be used for the descriptive analysis. The CVT-301-003 and CVT-301-009 rollover subjects will be excluded for MMRM analysis.

In addition, the changes in the spirometry values within treatment arm in CT-301-004 (CVT-301 vs Placebo) and differences between the CVT-301-004 treatments (CVT-301 vs Placebo) will be estimated with MMRM. The model will include the treatment group (CVT-301 DL1 or CVT-301 DL2), CVT-301-004 treatment, visit (visits at 1, 3, 6, 9, and 12 months), the stratification variables (Hoehn and Yahr stage and screening FEV1 and/or FEV1/FVC) and the interaction between CVT-301-004 treatment and visit as fixed factors. The baseline spirometry value will be included as a covariate. An unstructured covariance structure will be applied for MMRM. In case the model will not converge with the unstructured covariance structure, the heterogeneous compound symmetry (CSH) or the heterogeneous Toeplitz structure (TOEPH) will be used instead. If the unstructured covariance structure will be used, the denominator degrees of freedom will be computed using the Kenward-Roger method. In case of other covariance structures, the BETWITHIN option will be used for the denominator degrees of freedom. The least square (LS) mean, standard error, and LS mean difference for the changes from baseline within CVT-301-004 treatment, and between the CVT-301-004 treatment arm at each visit; along with the 95% confidence interval (CI) will be provided in a table. CVT-301-004 treatment arm difference will be assessed with a 2-sided alpha level of 0.05, unless specified otherwise.

The SAS code planned for the analysis is outlined below.

```
proc mixed data=&data;
class pdsevbl fevlbl trta stdygrp avisit usubjid;
model chg=base pdsevbl fevlbl stdygrp avisit trta stdygrp*avisit /
ddfm=kr;
repeated avisit / subject=usubjid(stdygrp) type=un;
lsmeans stdygrp*avisit / cl pdiff;
ods output Diffs=DIFF_MI LSMeans=LSM_MI tests3=tests ;
run;
```

The CVT-301-004 rollover patients in safety population will be used for the analysis.

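### Both spirometry/DLCO mixed models and the imputation include a Month 1 visit at which 004E schedules no such test, and FVC, a primary endpoint, has no model-based table

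*SAP*

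**What the plan says.** SAP 9.1 plans two MMRMs. The main one compares DL1 with DL2; the rollover one compares patients by their study 004 treatment. Both use "visit (visits at 1, 3, 6, 9, and 12 months), the stratification variables". The rollover model contains a study-group-by-visit interaction, and its output is to include the "LS mean difference for the changes from baseline within CVT-301-004 treatment, and between the CVT-301-004 treatment arm at each visit".

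The source of each visit is fixed in SAP 8, in a table introduced by "In general, for the purpose of the efficacy analyses, the visits will be pooled as follows". SAP 9 carries that table over to the lung function data: "For the statistical analysis of the spirometry data, the visits will be pooled as described in" that section. Under that table the 004 CVT-301 group takes Month 1 from 004 Week 4 and Month 3 from 004 Week 12. Former placebo, naïve and 005 observational-arm patients take Month 1 from the 004E Month 1 visit.

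On collection, once TV1 is past, SAP 9.1 has the pulmonary sites test patients at these times: "within 2 weeks prior to the 3-, 6-, 9-, and 12-month visits, and 4 to 5 weeks following completion of Treatment Visit 6". Protocol 11.1.6, after naming screening and TV1, states "All other spirometry assessments will be collected during the DLco and spirometry visits that take place at the pulmonary function lab". The schedule headed "Appendix 6: Time and Events Table-Treatment Visit 2 (TV2) for all Patients" has no row for performing either test; it only books the later ones.

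On FVC, SAP 4.1 names FEV1, FVC and FEV1/FVC as primary endpoints, in line with the primary objective in both documents. SAP 6.3 makes MMRM the primary spirometry analysis and multiple imputation its sensitivity analysis. The main MMRM and the imputation in SAP 9.1 name only FEV1, FEV1/FVC and DLCO. The rollover text is broader: "the changes in the spirometry values within treatment arm in CT-301-004 (CVT-301 vs Placebo").

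**The concern.** The pooling table was written for efficacy variables. Month 1 is a real visit there, because diaries and scales are collected at TV2. Applied to spirometry and DLCO, it creates a visit with no scheduled observation in two of the three study groups. A contrast the plan promises then cannot be delivered. If study 004 Week 4 data are used, the main model's Month 1 dose-group means could be taken to describe all patients although they come from one study group.

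The FVC gap is separate. A primary endpoint does not receive the method that the plan names as primary for incomplete spirometry, while DLCO, which SAP 4.3 lists only as a safety endpoint, receives the full set of models. On the plan's own figures, (390 − 290)/390 = 25.6% of enrolled patients may not complete, so how missing values are handled matters for a 12-month estimate.

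**Working it through.** There is no plan figure to reproduce; SAP 3.5 says the sample size has no formal statistical basis. The check is one of estimability, followed by a count of tables.

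**Can any Month 1 value arise in the former placebo or naïve groups?** The pooling table marks all study 004 visits of the former placebo group as not used. SAP 6.4 moves early-termination safety data only to a time point where that assessment was scheduled, and it does not re-assign visits by date. SAP 6.1 keeps unscheduled tests out of summary tables. Under the current schedule, none arises.

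**Rollover model.** The effects are baseline value, two binary strata, dose, and study group crossed with visit. The interaction spans the occupied group-by-visit cells, so

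rank = 4 (baseline, two strata, dose) + number of occupied cells.

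A cell mean or difference is estimable only if adding its row leaves the rank unchanged. The documents do not say which study 004 data exist, so all four cases are shown.

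| 004 data entering | Cells (former CVT-301 + former placebo) | Rank | Month 1 difference | Month 3 difference |
|---|---|---|---|---|
| Weeks 4 and 12 | 5 + 4 = 9 | 13 | not estimable (14) | estimable |
| Week 4 only | 4 + 4 = 8 | 12 | not estimable (13) | not estimable (13) |
| Week 12 only | 4 + 4 = 8 | 12 | no Month 1 level | estimable |
| Neither | 3 + 4 = 7 | 11 | no Month 1 level | not estimable (12) |

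The figure in brackets is the rank after adding the row. In the first two cases the former placebo Month 1 mean fails in the same way as the difference. Months 6, 9 and 12 are estimable in all four. With the visit factor starting at Month 3 and Week 12 data present, the rank is 4 + 8 = 12 and every mean and difference is estimable. Starting at Month 6, it is 4 + 6 = 10 and all are estimable with or without Week 12 data.

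**Main model, Week 4 data entering.** The effects are baseline, two strata, three study groups (main effect only) and dose crossed with visit: rank = 3 + 2 + 10 = 15. The Month 1 dose means are estimable, but only because study group is assumed to act equally at every visit. The planned code requests default LS means, which weight the three study groups 1/3 each. Two have no scheduled Month 1 data, so 2/3 of that weight is extrapolated. In the DL1-DL2 difference each study-group coefficient is 1/3 − 1/3 = 0, so study group cancels.

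**Imputation.** SAP 9.1 first fills intermittent gaps by MCMC, then imputes the remaining monotone gaps by sequential regression starting at Month 1. A former placebo or naïve patient with a later value gets Month 1 from the MCMC step; one with no later value gets it from the regression. Neither study group has a scheduled Month 1 observation to inform the value. After the MCMC step the regression has intercept 1 + baseline 1 + strata 2 + dose 1 + study group 2 = rank 7, so it can be fitted.

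**Table count (SAP 14, pulmonary function facility).**

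- FEV1: 6 MMRM + 1 imputation = 7
- FEV1/FVC: 6 + 1 = 7
- DLCO: 6 + 1 = 7
- FVC: 0, with 8 descriptive tables (2 overall, 2 on the ATS-quality subset, 2 excluding high-variability patients, 2 of change categories)

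SAP 11, which lists changes from the protocol, does not mention FVC. Protocol 12.5 plans an MMRM for spirometry values and lists FVC among the spirometry variables.

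**The case against.** The indexed MMRM tables are labelled as pulmonary function facility data, and in 004E facility testing after TV1 begins at Month 3. If only such data enter, no Month 1 record exists, the software creates no Month 1 level, and nothing is flagged. That stands. In that case the defect is a promise in the text that yields no output; a flagged non-estimable cell needs 004 Week 4 data.

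Earlier protocol versions are not supplied, and patients enrolled under them continue in the study. The SAP also plans neurology-site changes from baseline at later visits, which the current schedule would not generate. A reader might infer that no former placebo or naïve patient can have a Month 1 value. The documents support that only for the current schedule.

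A reader might also infer that the Month 1 imputation regression cannot be fitted. It can, because MCMC values are already in its input. The weakness is that those values have no scheduled observation behind them in two study groups.

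The practical effect is small: SAS would mark a non-estimable cell and not print a wrong number, and the aim is a 12-month description. That stands too. Dropping Month 1 would also remove real early data from actively treated patients from the model, although these can be shown descriptively.

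On FVC, SAP 9.1 is more specific than SAP 6.3, and the protocol's comparison by study 004 treatment names only FEV1 and the ratio. Against this, the SAP's version of that objective adds FVC, and SAP 6.3 exempts the primary endpoint from its rule against imputing safety data. Nowhere does the plan give a reason for leaving FVC out. It would be too strong to say that FVC goes unanalysed: it has eight facility tables, and its mean change can be roughly inferred from FEV1 and the ratio.

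**Conclusion.** Both points hold, and both are correctable faults of specification. They do not undermine the study's main estimates.

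The Month 1 rollover difference cannot be produced under the current schedule, whatever study 004 measured. The Month 3 rollover contrast depends on 004 Week 12 data that the documents do not confirm. If Week 4 data enter the main model, its Month 1 dose means rest on one study group of three. This assumes the Section 8 pooling, default LS-mean weights and no Month 1 spirometry carried over from an earlier protocol version.

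FVC, one of three primary endpoints, has none of the 21 planned MMRM and imputation tables (7 for each of three parameters). This is a departure from the plan's own stated method. The size of any resulting bias is unknown, and nothing in the documents allows it to be estimated.

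**What to change.** Remove Month 1 from the visit factor of both MMRMs and from the imputation sequence. Show any 004 Week 4 spirometry or DLCO descriptively, for the 004 CVT-301 group only. For each parameter, confirm that 004 Week 12 data exist and enter the model before reporting the Month 3 rollover contrast; otherwise start that contrast at Month 6. Add FVC to the main MMRM, the rollover MMRM and the imputation, with seven tables matching those for FEV1.

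The cost is SAP wording, one check of study 004's schedule per parameter, and seven tables from existing code. The Month 1 model estimate is lost, as is the Month 3 rollover contrast if Week 12 data do not exist, though it could not have been estimated in that case. SAP 2 allows updates until database lock but treats analyses defined after the study 004 unblinding as exploratory, so the added FVC models may have to carry that label.

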## Statistical Analysis Plan

- Patients who have dyskinesia of a severity that would significantly interfere with their ability to participate or perform study procedures.
- Pregnant or lactating females or females wishing to become pregnant.
- Patients who have any known contraindication to the use of LD, including a history of malignant melanoma or a history of narrow-angle glaucoma.
- Patients who have had previous surgery for PD (including but not limited to cell transplantation) or plan to have stereotactic surgery during the study period. Patients who have had deep brain stimulation [DBS] will also be excluded unless the procedure was performed more than 6 months prior to study enrollment.
- Patients with a history of psychotic symptoms requiring treatment, or suicidal ideation or attempt within the prior 12 months.
- Patients who have cancer with the exception of the following: basal cell carcinoma or successfully treated squamous cell carcinoma of the skin; cervical carcinoma in situ; prostatic carcinoma in situ; or other malignancies curatively treated and with no evidence of disease recurrence for at least 3 years.
- Patients taking certain prohibited medications (see [protocol Section 9.4.2](#)).
- Patients with a history of drug or alcohol abuse within the prior 12 months.
- Patients with chronic obstructive pulmonary disease (COPD), asthma, or other chronic respiratory disease within the last 5 years
- Patients with any contraindication to performing routine spirometry or who are unable to perform a spirometry maneuver (see [Appendix 15](#) for a list of contraindications).
- Patients with a current history of *symptomatic* orthostatic hypotension despite adequate treatment.
- Patients with any condition that in the investigator's opinion would make patients unable to comply with study procedures or make them unsuitable for their participation in the study.
- Patients who have any clinically significant abnormality or finding from examination, tests, or history that may compromise patient safety. Potential issues of concern should be raised to the medical monitor during eligibility review.
- For new CVT-301 naïve patients, patients who have been treated with an investigational drug within 4 weeks or 5 half-lives (whichever is longer) prior to the beginning of the screening period (this includes investigational formulations of marketed products).

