### 3.6. TREATMENT ASSIGNMENT & BLINDING

This study is a randomized, dose-level blinded, multicenter study of inhaled CVT-301 for the treatment of up to 5 OFF episodes per day in PD patients experiencing motor fluctuations (OFF episodes). Following completion of SV2 and prior to randomization (for CVT-301-003, CVT-301-009, CVT-301-005 and other CVT-301-naïve patients), eligibility criteria will be reviewed by delegated staff. Sites must leave a minimum of 5 days between randomization and Treatment Visit 1.

Before TV1, patients will be assigned/randomized to treatment group [Dose Level (DL) 1, or 2]. Patients who received DL1 (target nominal dose of 35 mg LD FPD) in the CVT-301-004 study will receive DL1 (target nominal dose of 35 mg LD FPD) in this study, and patients who received DL2 (target nominal dose of 50 mg LD FPD) in the CVT-301-004 study will receive DL2 (target nominal dose of 50 mg LD FPD) in this study. Patients who received placebo in the CVT-301-004 study, CVT-301-003 patients, CVT-301-009 patients, and CVT-301-naïve patients (including CVT-301-005 observational arm patients) will be randomized in a 1:1 ratio to DL1 or DL2.

Upon confirmation of eligibility, the site will randomize an eligible patient using the Interactive Web Response System (IWRS). Randomization will be differentiated by the patient's Hoehn and Yahr PD disease severity scale rating (<2.5 versus ≥2.5) to balance for disease severity across each treatment group and by screening spirometry (FEV1 <60% of predicted or FEV1/FVC ratio <70% versus FEV1 ≥60% of predicted and FEV1/FVC ratio ≥70%). For the patients who received placebo in CVT 301 004, the differentiation of CVT 301 004 will be used. Patients and site staff will be blinded to treatment group.

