model chg=base pdsevl fevlbl stdygrp avisit trta trta*avisit / ddfm=kr;
repeated avisit / subject=usubjid(trta) type=un;
lsmeans trta*avisit / cl pdiff;
ods output Diffs=DIFF_MI LSMeans=LSM_MI tests3=tests ;
run;
```

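### Default LSMEANS weights make the within-dose spirometry change describe an equal-weight cohort, not the CVT-301-treated patients analysed

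*SAP*

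**What the plan says.** SAP 3.1 sets the primary objective as pulmonary safety in the patients treated with CVT-301. SAP 6.3 names the MMRM as the primary way to analyse spirometry with incomplete data. SAP 9.1 gives the code. The class statement is "class pdsevl fevlbl trta stdygrp avisit usubjid" and the model is "model chg=base pdsevl fevlbl stdygrp avisit trta trta*avisit / ddfm=kr". The LS means come from "lsmeans trta*avisit / cl pdiff".

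The study-group factor has three levels, described as "treatment/study group (patients who received inhaled CVT-301 in CVT-301-004 study, patients who received placebo in CVT-301-004 study and CVT 301 naïve patients". The spirometry factor separates FEV1 below 60% of predicted or FEV1/FVC below 70% from the rest (SAP 3.6). The text of 9.1 promises LS means, standard errors and 95% intervals for the change within each dose and overall. It does not say to which mix of strata and study groups they refer.

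A second model in 9.1, for the CVT-301-004 rollover patients, uses "lsmeans stdygrp*avisit / cl pdiff", also without an observed-margins option. There study group is the LS-mean effect, so it is not averaged over. The strata and dose are.

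**The concern.** An LS mean has to average over every class factor that is not in its own effect. Without an observed-margins option SAS gives the levels equal weight, however many patients each contains. Half of the cohort behind each within-dose estimate is then in the low-spirometry stratum, while the baseline covariate is held at its observed mean.

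The low stratum is plausibly a minority. Exclusions cover "Patients with chronic obstructive pulmonary disease (COPD), asthma, or other chronic respiratory disease within the last 5 years", and patients in the reduced spirometry range need a pulmonologist's review to enter. If so, the estimate leans on the stratum with least information. A reader who takes the within-dose LS mean as the average lung-function change in the treated patients would read a number that answers a different question, with more noise than necessary. This matters because the objective concerns change within treated patients, and a change in either direction bears on the safety conclusion.

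**Working it through.** **The plan's own figure.** There is no precision figure to reproduce. SAP 3.5 plans 390 enrolled for about 290 completers, which implies (390 - 290)/390 = 25.6% not completing, and says that the size does not come from a formal calculation. No SD, stratum share or study-group count is given.

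**Weights implied by the code.** Spirometry stratum 1/2:1/2; Hoehn and Yahr stratum 1/2:1/2; study group 1/3:1/3:1/3. The strata and study group enter additively, with no interaction with dose or visit.

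**Precision.** Take one visit with complete data and arms of equal size. Patients randomized in this study "will be randomized in a 1:1 ratio to DL1 or DL2", but former CVT-301 patients keep their CVT-301-004 dose, so equal arms are an approximation. With w the weights used, m the observed margins and V the unit-variance covariance matrix of the stratum coefficients,

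Var(LS mean of an arm) = s² [1/n_arm + (w - m)'V(w - m)].

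For the spirometry factor alone, with prevalence p, N patients and n_arm = N/2, V = 1/(N p(1 - p)). The SE ratio, equal weights over observed margins, is

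sqrt(1 + (0.5 - p)² / (2p(1 - p))).

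| Assumed p | (0.5 - p)² / (2p(1 - p)) | SE ratio |
|---|---|---|
| 5% | 0.2025/0.095 = 2.132 | 1.77 |
| 10% | 0.16/0.18 = 0.889 | 1.37 |
| 20% | 0.09/0.32 = 0.281 | 1.13 |
| 30% | 0.04/0.42 = 0.095 | 1.05 |

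The ratio is 1 at p = 50% and never below 1.

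The study-group weights alone give 1.00 if the groups are equal, 1.03 at 50/25/25, 1.16 at 60/30/10 and 1.19 at 20/10/70. With all three factors (assumed: 35% in the smaller Hoehn and Yahr level, study groups 50/25/25), inverting the full design gives 1.80, 1.41, 1.18 and 1.10 at the four prevalences.

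**Location.** Let β be the low-minus-normal difference in change, given baseline. The LS mean moves by (0.5 - p)β because of the spirometry factor. For an assumed β of -50 mL this is -22.5, -20, -15 and -10 mL at p = 5, 10, 20 and 30%. If β = 0 it is zero.

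**In millilitres.** Assume SD 250 mL and 145 patients per arm. The 95% half-width with observed margins is 1.96 × 250/sqrt(145) = 40.7 mL. With the spirometry factor weighted equally it is 72.0, 55.9, 46.1 and 42.6 mL.

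**Coverage of the analysed-population mean.** At p = 10% and β = -50 mL, the SE is 20.76 × 1.374 = 28.5 mL and the shift is 20/28.5 = 0.70 SE. Coverage is Φ(1.96 - 0.70) - Φ(-1.96 - 0.70), about 0.89. Across the four prevalences it runs from 0.89 to 0.93.

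**Dose difference.** The same stratum and study-group terms enter both dose LS means and cancel. The DL1-DL2 difference and its SE, sqrt(4/290) = 0.117 SD, are the same under either weighting.

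**The case against.** The strongest reply is that equal-weight LS means are the software default and a recognised target, that no decision threshold attaches to the within-group estimate, and that SAP 9.1 already summarises change from baseline by dose, overall and by study group. A large divergence would show against those tables. This limits the harm but does not settle the matter. The tables use observed cases, whereas SAP 6.3 relies on the MMRM to deal with incomplete data. The multiple-imputation analysis reruns a similar MMRM, so with the same LSMEANS statement it inherits the weighting.

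The reply is right about size. Prevalence, the other splits, the SD and the 50 mL difference are all assumed, and β has to persist after baseline adjustment. The plan admits patients with FEV1/FVC above 60% and below 70% after review, allows current smokers and stratifies on this factor, so a stratum as small as 5 or 10% is not established.

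A reader might infer that the planned interval is simply too wide. The code does not support that: it is a valid 95% interval for the equal-weight mean. Read as an interval for the analysed patients it can under-cover despite its width, as shown above.

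A reader might also expect the bare OM option to deliver the mean of all treated patients. By default it counts data rows, here patient-visits, so early dropouts count for less. The MMRM also leaves out the CVT-301-003 and CVT-301-009 rollovers.

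**Conclusion.** The point stands as a mismatch between target and estimate: the within-dose LS mean refers to a mix that no section of the SAP chooses or states, while the objective refers to the treated patients. It is not an error in the interval or in the dose comparison. Nor does it reach every primary endpoint: FVC is one in SAP 4.1 but is not among the variables that 9.1 puts into the MMRM.

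Under the one-visit, equal-arm approximation, the extra standard error from the spirometry factor runs from about 5% at a prevalence of 30% to 77% at 5%, and any shift is proportional to a stratum difference that the documents do not report. In the second model the averaging concerns only the strata and dose. Its comparison of former CVT-301 with former placebo patients is unaffected, for the same reason as the dose difference. The change is worth making because observed margins are, to this approximation, never less precise and they match the objective.

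**What to change.** State in SAP 9.1 that the within-group LS means refer to the observed patient mix of the MMRM population, without the CVT-301-003 and CVT-301-009 rollovers. Then:

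- In the first spirometry model, add `OM=` to the LSMEANS statement, pointing to a data set in which each patient of that population counts once. Use the same pooled margins for both doses.
- Add an `lsmeans avisit` statement with confidence limits and the same margins. The text promises an overall change that the printed code does not request.
- In the second model, build the margins for the strata and dose in the same way from the CVT-301-004 rollover patients.
- Apply the same rule to any within-group LS means from the efficacy MMRM in 8.1, for which the SAP prints no LSMEANS code, and to the multiple-imputation reruns.
- Keep the equal-weight LS means as a footnoted check.

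The cost is one small extra data set for each analysis population and a few words of code. The estimate will then describe this trial's own mix of strata and study groups, which should be said when it is compared with other studies.
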